9.1.1 Preventing, Identifying, and Handling Hemolyzed Samples

Hemolysis of blood specimens may result in spuriously high K⁺ levels, potentially leading to inappropriate up-titrating of patiromer/placebo or inappropriate down-titration or discontinuation of ACEi/ARB/ARNi or MRA in this study.

The Laboratory Manual provides detailed descriptions of the recommended phlebotomy, sample preparation and transportation procedures to minimize hemolysis. Upon receipt of each blood sample for K⁺ analysis, the central laboratory will perform a semiquantitative test to assess for evidence of hemolysis. Predefined criteria will be established for determining whether the test result is indicative of potential hemolysis. These criteria and the criteria for removing serum K⁺ values from analyses on the basis of hemolysis are described in the Laboratory Manual. When a central laboratory sample has been identified as hemolyzed after it has been received and processed by the central laboratory, the blood draw will not be repeated by the site personnel. The Statistical Analysis Plan (SAP) summarizes how the data analyses will account for the missing central laboratory K⁺ value. If a blood sample has been identified as hemolyzed by the site personnel (i.e., visual inspection) before it has been sent to the central laboratory, a repeat blood draw can be performed if the subject is still at the site.

When a blood sample, which will be used by the site for patiromer/placebo titration and subject management, is hemolyzed (e.g., by visual inspection of the local laboratory serum sample), the site will repeat the K⁺ measurement from a separate blood draw within 1 day in order to ensure accurate decision-making regarding management of K⁺.

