1.2 Study Design

The DIAMOND study is a prospective Phase 3b multinational, multicenter, double-blind, placebo-controlled, randomized withdrawal, parallel group study that includes screening and an up to 12-week Run-in Phase (all subjects will have patiromer initiated and RAASi medications, including MRA, optimized) and a randomized withdrawal Double-Blinded Treatment Phase. The primary efficacy assessment will be based upon the data collected during the Double-Blinded Treatment Phase.

During the Run-in Phase, which is single blind to the subject, the Investigator will manage RAASi initiation and/or dose escalation as recommended by practice guidelines, using clinical judgment to customize RAASi addition or dose escalation based on subject response. Assessment of serum potassium will occur at each visit. The patiromer dose will be titrated based on the subject's potassium level.

After completing the Run-in Phase and found eligible for the Double-Blinded Treatment Phase of the study, subjects will be randomized. Randomized subjects will begin treatment with patiromer or placebo using the same number of packets established for patiromer at the end of the Run-in Phase and will continue the RAASi regimen being administered at the end of the Run-in Phase.

The study will continue until reaching at least the Week 6 visit for each subject. An independent Data Safety and Monitoring Board (DSMB) will act in an advisory capacity to monitor the safety of subjects who participate in this study.

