2.2 General Considerations

Efficacy analyses will be performed by planned treatment (i.e. as randomized), and safety analyses by actual treatment received.

For continuous variables, descriptive statistics will include the number of subjects, mean, standard deviation (SD), standard error (SE), median, 25th and 75th percentiles, minimum and maximum.

For categorical variables, descriptive statistics will include frequencies and percentages in each category.

For time-to-event variables, the descriptive statistics will include the median, 95% CI, 25th and 75th percentiles, minimum and maximum. Counts (percentages) of subjects with events and of subjects censored will also be provided.

When mean change from baseline is summarized, subjects will only be included in the analysis if they have both a baseline value and a post-baseline value at the time point of interest.

Detailed statistical analyses are specified in sections below.

On June 24, 2021, sites were informed that the study would be closing and that subjects should be brought in for their End of Study (EoS) visit as soon as possible. After this date, many sites incorrectly began to titrate and/or discontinue blinded study drug medication prior to the EoS visit. Because this practice was wide-spread, data after June 24, 2021 will be censored for purposes of efficacy analyses. Sensitivity analyses, including data after June 24, 2021, will be conducted for the primary and key secondary endpoints. Safety and exposure analyses will primarily be conducted using all data. Some sensitivity analyses may be conducted using data only through June 24, 2021, as appropriate.

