2.10 Statistical Assessment of Efficacy Endpoints

2.10.1 Primary Analyses

The primary analysis will be based upon the mean change in serum K⁺ levels from Baseline and is analysed by means of a mixed model for repeated measures (MMRM) approach. The model will include data through the last scheduled visit for which at least 10% of subjects have assessments.

The primary analysis will include only local laboratory serum potassium data from assessments on or before June 24, 2021. A sensitivity analysis will be performed that also includes data after June 24, 2021.

All analyses will be restricted to serum K⁺ assessments and not substituted by plasma values as they are known to be systematically lower. A Gaussian linear model for repeated measures will be used, with treatment, geographic region, sex, baseline T2DM status, and visit as factors, and baseline K⁺ level, baseline eGFR as covariates. The error terms are assumed to follow a multivariate normal distribution with unstructured covariance. Least squares mean changes from Baseline will be reported for both treatment groups with 95% CIs, as well as the difference between the least squares group means with 95% CI and p-value testing the null hypothesis of no treatment effect.

Changes in treatment effect over follow-up time will be explored by including treatment by visit interactions in the above-mentioned model. In addition, sensitivity analyses accounting for potentially informative missingness will be based upon a Win Ratio approach [1, 2].

The following additional sensitivity analyses will be conducted by re-running the primary MMRM as follows:

- Using local serum potassium data without a cutoff at June 24, 2021
- Using both local and central serum potassium data on or before June 24, 2021 (if both values are present at a visit, the centrally assessed serum potassium will be used)
- Using only central serum potassium data on or before June 24, 2021:

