2.12 Baseline and Screening Definitions

2.12.1 Baseline

Unless otherwise specified, Baseline is defined as the value of a variable at the Day 1/Baseline Visit. If there is a missing value at the Day 1/Baseline Visit, Baseline is defined as the last available non-missing value on or before and ≤ 10 days prior to the first dose of blinded study medication.

For randomized but not treated subjects, Baseline is defined as the value at the Day 1/Baseline Visit; if missing, it is defined as the last available non-missing value on or before and ≤ 10 days prior to the date of randomization

Some laboratory tests are assessed by both the central laboratory and a local laboratory. In these cases, the following baseline values are defined:

- Local Baseline (Bsl_L) is defined as above using only local values
- Central Baseline (Bsl_C) is defined as above using only central values

- Central/Local Baseline (Bsl_CL) is defined as the Central Baseline (Bsl_C) if available, and as the Local Baseline (Bsl_L) if the Central Baseline is missing
- Local/Central Baseline (Bsl_LC) is defined as the Local Baseline (Bsl_L) if available, and as the Central Baseline (Bsl_C) if the Central Baseline is missing

In general, if an analysis includes only local laboratory test results for a specific laboratory test value, Bsl_L is used to calculate change from Baseline and is used as the baseline covariate in models; if the analysis includes only central laboratory test results, Bsl_C is used; if the analysis includes both central and local test results, Bsl_CL or Bsl_LC is used.

Tables and figures will specify what baseline is being used for the table or figure.

The following are specific exceptions to these rules:

- For eGFR, Bsl_CL is defined differently than for other laboratory parameters. The definition is: the value of the Central Baseline (Bsl_C); if missing, the value of the Local Baseline (Bsl_L); if missing, the value at Day 3, with preference for the central value
- Urine ACR is assessed only by the central laboratory, and is collected only during Run-in, at Day 3, Week 2, Week 18, and at each 3-month visit during the Double-blinded Treatment Phase. For analyses of proteinuria, Baseline is defined as the central value of urine ACR at the Day 3 Visit.

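### Does the central-laboratory-only rerun of the primary potassium model need a matched local-only run beside it?

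*SAP*

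**What the plan says.** The SAP fixes the data source of the primary model in section 2.10.1: "The primary analysis will include only local laboratory serum potassium data from assessments on or before June 24, 2021". Among the sensitivity analyses, it then introduces a list with "The following additional sensitivity analyses will be conducted by re-running the primary MMRM as follows". The three entries are local values without the date limit, local and central values together up to the date limit (central taken when a visit has both), and the one at issue, "Using only central serum potassium data on or before June 24, 2021". That last entry ends in a colon with nothing after it.

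SAP 2.12.1 ties the baseline to the source: "if the analysis includes only central laboratory test results, Bsl_C is used", and "if the analysis includes both central and local test results, Bsl_CL or Bsl_LC is used". It also says that each table and figure will state which baseline it uses.

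The sampling schedule is in the protocol. Potassium is measured both locally and centrally at Day 1 (8.2.1), at Week 18 and every three months after that (8.2.6), and at the end-of-study visit (8.4). It is measured only locally at Day 3, Week 1, Week 2 and Week 6 (8.2.2 to 8.2.5) and at unscheduled visits (8.3). The Schedule of Events agrees.

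On follow-up, SAP 1.2 says "The study will continue until reaching at least the Week 6 visit for each subject", and SAP 2.2 says "data after June 24, 2021 will be censored for purposes of efficacy analyses". Protocol 9.1.1 adds that for a central sample found hemolyzed at the central laboratory, "the blood draw will not be repeated by the site personnel".

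**The concern.** The central-only entry is presented as the primary model run on other data, so a reader may take any difference from the primary as a laboratory effect. Three other things change with it.

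- **Timing.** The primary averages the treatment effect from Day 3 onward; the central-only run averages it from Week 18 onward. The model has a treatment main effect and no treatment-by-visit term, so if the effect changes over time the two runs estimate different averages.
- **Subjects.** Anyone who had not reached Week 18 by June 24, 2021 has no scheduled post-baseline central value. End-of-study visits were called on that date, so few of their central values can enter. Hemolyzed central samples also drop out.
- **Baseline.** The central baseline replaces the local one.

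The question of laboratory source matters because Protocol 3.2 and 12.8.1 prefer central values when a visit has both, whereas the SAP's primary uses local values only. The central-only rerun is the one planned check with no local potassium in it. A gap from the primary could be mistaken for a laboratory effect, or a real laboratory effect could be masked by timing. The suggested remedy is a local-only run restricted to the subject-visits that also have a central value.

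**Working it through.** **The plan's own figure.** With difference 0.116, SD 0.5, two-sided 5% and 90% power (SAP 1.5), n per arm = 2 × (1.960 + 1.282)² × 0.5² / 0.116² = 2 × 10.507 × 0.25 / 0.013456 = 390.4, so 391. Allowing for 5% loss gives 391 / 0.95 = 411.6 (412), or 391 × 1.05 = 410.6 (411). The stated 410 reproduces within two subjects. The SAP gives no figure for the central-only rerun.

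**What each contrast estimates.** Let δ(v) be the treatment effect at visit v on local values. Let λ be any shift in that effect when central values are used, taken as constant from Week 18. Let w(v) be the primary's weights over all visits and u(v) the weights over Week 18 onward, each set summing to 1. W is the part of w that falls on Week 18 onward.

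- Central-only minus primary = [Σ u(v)δ(v) − Σ w(v)δ(v)] + λ. The bracket is timing and is zero only for particular profiles, such as a constant effect.
- Central-only minus matched local-only = λ.
- Local-plus-central minus primary, with the same weights = W × λ. Values before Week 18 are the same in both runs and cancel, so timing drops out whatever the profile.

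**Size of the timing term.** Inputs from the SAP are 410 per arm and SD 0.5. The effect profiles, attendance, correlations and laboratory noise (SD 0.1 to 0.2 per value) are assumed. Attendance is 100% to Week 6, then falls linearly to between 10% and 60% at a last visit between Week 31 and Week 70. Over 160 scenarios with identical laboratories, central-only minus primary (as placebo minus patiromer) is:

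| Effect over time | Expected gap, mEq/L |
|---|---|
| Rises, then holds | +0.012 to +0.057 |
| Rises, then fades | −0.033 to +0.011 |
| Constant | 0 |

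The standard error of that gap is 0.012 to 0.040. The gap exceeds 1.96 standard errors only in the steepest profile (no effect at Day 3, full effect at Week 6), and there in about half the scenarios. A simulation with an estimated unstructured covariance (300 runs, steepest profile, last visit Week 44 at 25% attendance) gave +0.050 (SD 0.026) for central-only minus primary and +0.001 (SD 0.015) for the matched pair. So the confounding is real in principle.

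**The planned alternative against the proposed one.** On a similar grid of 288 scenarios:

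| Contrast | Expected gap if laboratories agree | Standard error of gap |
|---|---|---|
| Central-only minus primary | non-zero if timing matters | 0.012 to 0.041 |
| Central-only minus matched local-only (proposed) | 0 | 0.005 to 0.025 |
| Local-plus-central minus primary (planned) | 0 | 0.002 to 0.006 |

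The planned contrast shows W × λ, with W between 0.13 and 0.60. To compare like with like, divide its standard error by W in each scenario. The result is 0.93 to 1.09 times the matched pair's standard error, median 0.99. The two contrasts are about equally able to detect a laboratory effect from Week 18 onward.

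The scaling by W has a useful reading. If λ were 0.046, an assumed value, the primary estimate would move by 0.13 × 0.046 = 0.006 up to 0.60 × 0.046 = 0.028. That is how much the choice of laboratory alters the primary result, and the local-plus-central rerun reports it directly. Its central-preferred rule is also the rule in Protocol 3.2 and 12.8.1, so it answers whether the SAP's switch to local values matters.

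**The case for a change.** The strongest case for the extra run is that it is nearly free and cleaner. It needs one more model fit, leaves the primary untouched, and gives λ on identical subject-visits. A small gap between central-only and primary can also mislead. In an illustration with assumed inputs, a raw gap of 0.010 concealed a laboratory component of +0.060 offset by −0.051 from timing and subjects (they sum to 0.009; the rest is rounding). The local-plus-central rerun has its own blemishes. Its early values stay local, the choice between Bsl_CL and Bsl_LC is left open, and two separately fitted models will not have exactly equal weights. The standard errors above also leave out baseline laboratory noise; the simulated matched value was 0.014 to 0.015 against 0.012 analytically.

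It stands that central-only against primary is not a laboratory comparison and should not be reported as one. The rest does not separate the proposal from what is planned. The matched pair cannot check Day 3 to Week 6 either, since no scheduled central values exist there. It changes baseline too, from Bsl_L to Bsl_C. In both contrasts, a laboratory offset common to the two arms cancels from the treatment difference, because allocation is randomized and baseline is a covariate. The open baseline label is settled when the tables state it, as SAP 2.12.1 requires. The masking example concerns the central-only contrast, whereas the local-plus-central contrast has no timing term.

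**Conclusion.** The observation about sampling is correct, but the change brings no material gain. Nothing in SAP 2.10.1 says the central-only rerun isolates laboratory source, and no number, rule or conclusion in the plan is wrong if it is followed. An analyst who wants to comment on laboratory source already has a planned contrast, local-plus-central against the primary. It is free of timing effects and about as sensitive from Week 18 onward as the proposed pair (ratio 0.93 to 1.09, median 0.99). The planned treatment-by-visit model and the by-visit changes show separately whether the effect moves over time. The matched local-only run is a reasonable optional supplement.

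This rests on assumed visit profiles, attendance, correlations and laboratory noise, because the documents give none of these. It also assumes nearly equal weights in the two fitted models and leaves out baseline laboratory noise. It takes the visible text of the central-only entry as complete; if text after the colon already fixes the visits, the concern has even less to stand on. The primary model, its test, alpha and sample size are not affected either way.

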2.10.2 Secondary Endpoint Analyses

Key secondary efficacy endpoints will be tested sequentially in the order listed below (i.e. fixed-sequence method to preserve the familywise type I error rate) using the full analysis set, and will be summarized descriptively through the calculation of point estimates by treatment group along with 95% confidence intervals (CI) for the treatment differences.

For each key secondary endpoint, the primary analysis will use only data through June 24, 2021. A sensitivity analysis that includes all data will also be performed for each key secondary endpoint.

The following lists the secondary endpoints and the analysis methods to be used:

- Hyperkalemia events: The time to the first event of hyperkalemia with a serum K+ value >5.5 mEq/L, as per the measured values from the central or local laboratories, is analysed using a Cox proportional hazards regression model. The treatment difference will be reported as hazard ratio (HR) with 95% CI and p-value from a Wald-type test considering the null hypothesis that the HR is equal to 1. The event probabilities will be estimated using the Aalen-Johansen estimator of the cumulative incidence function accounting for competing events such as death.
- Durable enablement to stay on the MRA target dose (50 mg spironolactone or eplerenone): The time to the first event of reduction of the MRA dose below target is analysed using a Cox proportional hazards regression model. The treatment difference will be reported as hazard ratio (HR) with 95% CI and p-value from a Wald-type test considering the null hypothesis that the HR is equal to 1. The event probabilities will be estimated using Aalen-Johansen estimator of the cumulative incidence function accounting for competing events such as death.

Note: Discontinuation of the target dose for at least 14 days (or less if at the EoS) is required to confirm this endpoint.

- Investigator reported AEs of hyperkalemia (first and recurrent) are analysed using a negative binomial regression with the logarithm of the individual follow-up time as offset. The treatment difference will be reported as rate ratio (RR) with 95% CI and p-value from a Wald-type test considering the null hypothesis that the RR is equal to 1. A joint frailty model of the total (first and recurrent) hyperkalemia events and time to death as terminating event may be implemented. If all-cause mortality is substantial in number and differential between the treatment groups, then the joint frailty model would become the main analysis approach.
- Hyperkalemia-related hard outcomes are analysed using the un-matched Win Ratio approach with the following hierarchical components (all assessed during comparable follow-up times):
 1. Time to CV death
 2. Total number of CV hospitalizations
 3. Total number of hyperkalemia toxicity events with serum K+ >6.5 mEq/L
 4. Total number of hyperkalemia events with serum K+ $>6.0-6.5$ mEq/L
 5. Total number of hyperkalemia events with serum K+ $>5.0-6.0$ mEq/L

A death with cause classified as “undetermined” by the event adjudication committee will be considered as a CV death.

- RAASi Use Score will be analysed using the Win Ratio approach for each pair of patients at the end of the comparable follow-up period that is appropriate for that pair of patients, based on the following additive components. Points are accumulated from two components at the respective time for each patient in each comparison:

Component A:

- If during the follow-up (to the respective end of follow-up in the comparator subject) there was a death, the subject is assigned 0 points

- If during the follow-up (to the respective end of follow-up in the comparison) there was a CV hospitalization, but the subject is alive at the end of that follow-up, the subject is assigned 1 point
- If during the follow-up (to the respective end of follow-up in the comparison) there was no CV hospitalization and the subject is alive at the end of that follow-up, the subject is assigned 2 points

Component B:

Further points are collected for the treatment status at the respective end of follow-up in the comparison:

- For ACEi/ARB/ARNi use: >50% of the target dose = 2 points
- For ACEi/ARB/ARNi use: >0 and up to 50% of the target dose = 1 point
- For MRA use: >50% of the target dose = 2 points
- For MRA use: >0 and up to 50% of the target dose = 1 point
- For beta-blocker use: >50% of the target dose = 2 points
- For beta-blocker use: >0 and up to 50% of the target dose = 1 point

In summary, each subject in each comparison can have 0-8 points (sum of Components A and B) and all subjects are compared using this score at the respective appropriate follow-up time point.

Regression analyses will be adjusted for geographic region as the stratification factor of the randomization and relevant baseline characteristics of the subjects.

For analyses based upon the negative binomial distribution, the subject level count data will be modelled as a function of treatment with the natural log of the subject level follow-up time taken into account in the estimation of the event rate.

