12.3 Randomization

Subjects will be randomized to the treatment arms (1:1 assignment) using permuted block randomization stratified by geographic region. Randomization will take place using a centralized list accessed electronically via IWRs on the day of randomization, after randomization eligibility is determined.

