 5. Total number of hyperkalemia toxicity events with serum $K^+ > 5.0-6.0$ mEq/L
- RAASi Use Score which will be analyzed using the Win Ratio approach for each pair of patients at the end of the comparable follow-up period that is appropriate for that pair of patients with the following additive components. Points are accumulated from two components at the respective time for each patient in each comparison:

Component A:

- If during the follow-up (to the respective end of follow-up in the comparison) there was a death, the subject is assigned 0 points
- If during the follow-up (to the respective end of follow-up in the comparison) there was a CV hospitalization, but the subject is alive at the end of that follow-up, the subject is assigned 1 point
- If during the follow-up (to the respective end of follow-up in the comparison) there was no CV hospitalization and the subject is alive at the end of that follow-up, the subject is assigned 2 points

Component B:

Further points are collected for the treatment status at the respective end of follow-up in the comparison:

- For ACEi/ARB/ARNi use: $>50\%$ of the target dose = 2 points
- For ACEi/ARB/ARNi use: >0 and up to 50% of the target dose = 1 point
- For MRA use: $>50\%$ of the target dose = 2 points
- For MRA use: >0 and up to 50% of the target dose = 1 point
- For beta-blocker use: $>50\%$ of the target dose = 2 points

- For beta-blocker use: >0 and up to 50% of the target dose = 1 point

In summary, each subject in each comparison can have 0-8 points (sum of Components A and B) and all subjects are compared using this score at the respective appropriate follow-up time point.

The regression analyses will be adjusted for geographic region as the stratification factor of the randomization and relevant baseline characteristics of the subjects.

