1.3 Method of Assigning Subjects to Treatment Groups

Subjects will be randomized to the treatment arms (1:1 assignment) using permuted block randomization stratified by region. Randomization will take place using a centralized list accessed electronically on the day of randomization after Double-Blinded Treatment Phase eligibility is determined (Day 1).

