2.16 Pooling Strategy for Strata

The number of subjects randomized is quite large relative to the number of strata. As such, no pooling of strata is planned for data analysis.

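### Region, the only randomization stratum, is not used in the win ratios for key secondary endpoints 4 and 5: a small loss of efficiency, not a bias

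*SAP*

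**What the plan says.** Region is the only stratification factor. Protocol 12.3 describes "permuted block randomization stratified by geographic region" and SAP 1.3 has "permuted block randomization stratified by region".

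The plan then carries region into most of the confirmatory analyses. It is a factor in the primary MMRM (SAP 2.10.1). SAP 2.10.2 adds: "Regression analyses will be adjusted for geographic region as the stratification factor of the randomization". Protocol 12.8.2 says the same: "The regression analyses will be adjusted for geographic region as the stratification factor of the randomization". That covers the Cox models for key secondary endpoints 1 and 2 and the negative binomial model for endpoint 3.

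Endpoints 4 and 5 are win ratios. For endpoint 4: "Hyperkalemia-related hard outcomes are analysed using the un-matched Win Ratio approach with the following hierarchical components". For endpoint 5 (the RAASi Use Score): "all subjects are compared using this score at the respective appropriate follow-up time point". Neither description mentions region, strata or weights, and neither is redacted. Both endpoints are confirmatory: "Key secondary efficacy endpoints will be tested sequentially in the order listed below".

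SAP 2.16 says "The number of subjects randomized is quite large relative to the number of strata" and concludes that strata will not be pooled, but it does not say which analyses use strata. SAP section 3, which lists departures from the protocol, is silent on this.

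**The concern.** A win ratio is not a regression, so the adjustment sentence does not reach endpoints 4 and 5. Three of the five confirmatory secondary tests respect the randomization stratum and two do not, with no reason given.

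Blocking within region balances the arms on region and so removes between-region variation from the treatment comparison. An unstratified standard error still counts that variation. If region is prognostic, the standard error is too large for the design and the test rejects less often than its nominal level. Cross-region pairs are also decided partly by region rather than by treatment, which pulls the win ratio toward 1.

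At stake is some power on the last two tests of the sequence. There is also an ambiguity: excluding matched pairs does not exclude strata, so two analysts could derive different confirmatory p-values from the same SAP.

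**Working it through.** **Inputs from the documents.** 820 subjects, 1:1, two-sided 5% (SAP 1.5); permuted blocks within region (SAP 1.3); a 0-8 score for endpoint 5 (SAP 2.10.2). Region sizes, block size, event rates, win-ratio effects and the prognostic strength of region are not given. They are assumed below and varied.

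**The plan's own figure.** The only sizing is for the primary endpoint. n per arm = 2(1.960 + 1.282)² × 0.5² / 0.116² = 391. Allowing for 5% loss gives 391/0.95 = 412 or 391 × 1.05 = 411, against the stated 410. At 410 × 0.95 = 389.5 evaluable per arm, power is 89.9%. The figure reproduces; there is none for the win ratios.

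**Step 1: normal approximation.** Let r be the share of outcome variance lying between regions. The true variance of the unstratified estimate is (1 - r) times the variance used in the test.

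- Type I error = 2Φ(-1.960/√(1 - r))
- Power where the stratified test has 80% = 1 - Φ(1.960/√(1 - r) - 2.802)

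| r | Type I error, unstratified | Power, unstratified (stratified 80%) |
|---|---|---|
| 2% | 4.8% | 79.4% |
| 5% | 4.4% | 78.5% |
| 10% | 3.9% | 76.9% |
| 20% | 2.8% | 72.9% |

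For r = 5%: 1.960/√0.95 = 2.011, so type I error is 4.4% and power is 1 - Φ(-0.791) = 78.5%.

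**Step 2: simulated ordinal score.** 820 subjects, four regions (equal, or 60/110/200/450), blocks of 4. The null win ratio was 1.00 for both analyses. Without strata, power fell by about 0.4 points at r = 2%, 1.1-1.4 at 5%, 2-3.4 at 10% and 5.4-6.3 at 20%. This agrees with Step 1.

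**Step 3: simulations built on each endpoint.** Assumptions: regions of 370/205/164/81 (45/25/20/10%), blocks of 4, follow-up uniform over 2-18 months, each pair compared at its shorter follow-up, log win ratio with U-statistic variance, 6,000 replicates. SAP 2.15 labels regions A to D but does not say that they are the strata.

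*Endpoint 4.* Monthly rates: CV death 0.005, CV hospitalization 0.012, K+ >6.5 0.004, >6.0-6.5 0.010, >5.0-6.0 0.120. Gamma frailty variance 1 on the counts; hyperkalemia rate ratio 0.63; no effect on death or hospitalization. All rates are multiplied by a regional factor.

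| Highest-to-lowest regional rate | Power, unstratified / stratified (%) | Change | Null rejection (%) |
|---|---|---|---|
| none | 81.7 / 81.3 | -0.4 | 4.8 / 4.7 |
| 2-fold | 79.8 / 80.2 | +0.4 | 4.8 / 5.1 |
| 3-fold | 78.8 / 79.9 | +1.1 | 4.3 / 4.8 |
| 4-fold | 76.9 / 78.9 | +2.0 | 4.2 / 5.1 |
| 5-fold | 74.2 / 77.0 | +2.8 | 3.7 / 4.9 |

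*Endpoint 5.* Monthly hazards: death 0.006, CV hospitalization 0.012, MRA reduction 0.03, MRA stop 0.012, ACEi/ARB/ARNi reduction 0.012. Hazard ratio 0.45 on the three dose changes. What varies by region is the share of subjects above 50% of target dose.

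| Regional range of that share | Power, unstratified / stratified (%) | Change |
|---|---|---|
| none | 69.0 / 68.7 | -0.3 |
| beta-blocker, 40-60% | 69.3 / 69.2 | -0.1 |
| beta-blocker, 30-70% | 69.2 / 70.1 | +0.9 |
| beta-blocker, 20-80% | 69.2 / 71.3 | +2.1 |
| beta-blocker and ACEi/ARB/ARNi, 40-60% | 67.8 / 68.7 | +0.9 |
| both, 30-70% | 66.2 / 69.9 | +3.7 |
| both, 20-80% (extreme) | 64.9 / 73.4 | +8.5 |

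Null rejection with no spread and with both shares varying was 4.7/4.6, 4.8/4.9, 4.3/5.0 and 3.2/4.9%. Monte Carlo error is 0.1-0.4 points for the power differences and about 0.3 for null rejection. Effects were chosen only to put power near 70-80%.

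**Where the gain comes from.** Stratifying makes the log-scale standard error 0.2-3.7% larger, but the estimate is less attenuated: 1.344 against 1.323 for endpoint 4 at 5-fold, and 1.289 against 1.270 for endpoint 5 with both shares at 30-70%. Under the null, mean estimated SE divided by empirical SD rises from 1.02 to 1.06 (endpoint 4) and to 1.08 (endpoint 5) without strata, and stays at 0.99-1.02 with them.

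**Other layouts.** Gains for endpoint 4 at 3-fold and endpoint 5 with beta-blocker share 30-70%: two regions 70/30, +3.1 and +2.0; four equal regions, +1.6 and +0.9; eight regions, +0.5 and +0.3.

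**The case against.** The strongest reply is that nothing is broken. The all-pairs test is valid, a conservative test breaches no error guarantee, and only the last two tests in the sequence are touched. All of that stands.

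It also stands that no passage shows region to be prognostic. The documents offer only a possible route for endpoint 5. The beta-blocker item is worth up to 2 of 8 points, any dose or documented intolerance qualifies at entry (Protocol 5.2), the run-in optimizes only ACEi/ARB/ARNi and MRA (6.7.2), and other medication continues as at entry (6.8.4). Those passages allow differences between subjects; they do not show differences between regions. The run-in aim of full target doses, and the dose requirements for randomization in Protocol 5.4, also limit spread in the RAASi items. In the modest scenarios the change is between a loss of 0.4 points and a gain of about 1.

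Stratifying also changes the quantity estimated. With 45/25/20/10% shares, 1 - (0.45² + 0.25² + 0.20² + 0.10²) = 0.685 of all pairs are cross-region and would no longer be compared (42% with two regions 70/30, 84% with eight). The less attenuated win ratio is a different estimand, not the correction of a bias. The endpoint 5 wording sits closer to an all-pairs comparison than the endpoint 4 wording does, and SAP 2.16 could be read as implying that strata are kept somewhere.

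Finally, the SAP names no test or variance for either win ratio, so the conservatism calculated above is that of the usual U-statistic variance. This supports stating the method in full. These objections limit the severity; they do not show that leaving the stratum out is the better choice.

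**Conclusion.** The concern holds as a low-severity improvement, not as an error in the plan. The confirmatory win ratios for endpoints 4 and 5 have no stated region strata, although region is the randomization stratum and is used in every other confirmatory analysis.

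The unstratified test is unbiased between arms under the null. If region is prognostic, it is mildly conservative, at about 3.8-4.8% when region explains 2-10% of outcome variance. Stratifying brings rejection back to about 5%, gains roughly 0-4 points of power unless regions differ extremely, and costs at most about 0.4 points if they do not differ. These sizes depend on assumed region sizes, event rates and effects; the direction does not. The main analyses of the primary endpoint and of endpoints 1 to 3 are unaffected.

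**What to change.** Before unblinding, amend SAP 2.10.2 so that the main analysis of endpoints 4 and 5 is a win ratio comparing pairs only within randomization region.

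- **Estimator.** With W_s wins, L_s losses and N_s subjects in region s, use WR = Σ(W_s/N_s) / Σ(L_s/N_s). This is the same as weighting within-region win and loss proportions by n1·n2/(n1 + n2).
- **Inference.** Name the test, and use the matching stratified U-statistic variance for log WR with its 95% CI.
- **Sensitivity.** Keep the all-pairs win ratio for both endpoints.
- **Consistency.** Apply the same stratification to the win-ratio sensitivity analysis of the primary endpoint in SAP 2.10.1. No calculation was made for that analysis; the reason is consistency only.

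If the sponsor prefers the all-pairs version as the main analysis, the SAP should at least say that no strata are used and give the test and variance.

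The cost is SAP wording and minor programming, with no new data. Within-region pairs become the target of inference, the log-scale standard error is slightly larger, and a little power is lost if regions do not differ. SAP 2.16 describes the sample as large relative to the strata, so sparse regions are not expected.
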